### **3.1.6. Handling of Missing/Incomplete Date/Time**

All analyses of AEs will be based on the principle of treatment emergence. Treatment emergent adverse events (TEAEs) are defined as new or worsening adverse events occurring on or after the first administration of study treatment until 30 days after the last dose of study treatment or before the start of subsequent therapy, whichever comes first. For missing or incomplete AE start dates, the following criteria will be used to determine whether an AE is treatment emergent:

Missing AE start day:

- If the partial date contains a different month or year from the date of first study dose, then impute it as the first day of the month.
- If it contains the same month and year as the date of first dose, then impute it as date of first dose.

Missing AE start day and month:

- If the partial date contains a different year from the date of first dose, then impute the missing day and month as Jan 01.
- If it contains the same year as the date of first dose, then impute the missing day and month as day and month of first dose.

Completely missing AE date:

- Missing date will not be imputed and AE is considered treatment emergent.

A medication will be considered concomitant if it is taken on or after the date of first dose of study treatment. In order to determine whether a medication with an incomplete or missing start or end date is concomitant, the following criteria will be used:

- If the start date of a medication is on or after the first dose date and the stop date of the medication is missing, that medication is considered concomitant.
- If the start date of a medication is missing and the stop date of that medication falls on or after the first dose date, that medication will be considered concomitant.
- If the start date of a medication is prior to the first dose date and the stop date of the medication is missing, that medication is considered not concomitant.
- If the start date of a medication is missing and the stop date of the medication is prior to the first dose date, that medication is considered not concomitant.
- If both the start and stop dates of a particular medication are missing, that medication will be considered not concomitant.

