7.3.2.4. Concomitant Medications

Prior and concomitant medications will be coded to the generic term using the current version of the World Health Organization (WHO) Drug Dictionary and listed by patient.

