### **3.5.3. Concomitant Medications/Therapies**

Concomitant medications are those taken on or after the date of first dose of study treatment or those started before the first dose of study drug and are continuing at the time of the first dose of study drug. All medications taken from 28 days prior to enrollment through 30 days following the last dose of study drug will be recorded in the eCRF. Similarly, surgeries or palliative radiotherapy that are undergone 28 days prior to enrollment through 30 days following the last dose of study drug will be recorded in the eCRF.

Concomitant medications will be coded using the World Health Organization (WHO) Drug Dictionary Enhanced (WHO-DDE, Version B3 September 2021) and classified by Anatomical Therapeutic Class (ATC) Level 3 and PT. Frequencies and percentages of patients using each concomitant medication will be presented for each cohort and overall for the Safety Analysis Set.

The summary will be sorted alphabetically by ATC level 3 term, and within ATC level 3 term, by decreasing PT frequency for all patients.

All concomitant medications and therapies will be presented in patient listings.

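### SAP 3.1.6 classes a medicine started before first dose with no stop date as not concomitant, against the definitions in the same paragraph and in SAP 3.5.3

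*SAP*

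**What the plan says.** The medication paragraph of SAP 3.1.6 opens with a definition: "A medication will be considered concomitant if it is taken on or after the date of first dose of study treatment". It then gives five bullets to decide "whether a medication with an incomplete or missing start or end date is concomitant". The third bullet deals with a start date that is "prior to the first dose date and the stop date of the medication is missing, that medication is considered not concomitant". The fifth says: "If both the start and stop dates of a particular medication are missing, that medication will be considered not concomitant".

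SAP 3.5.3 defines concomitant medicines again. Besides those taken on or after first dose, it includes "those started before the first dose of study drug and are continuing at the time of the first dose of study drug". It then specifies the output: "Frequencies and percentages of patients using each concomitant medication will be presented for each cohort and overall for the Safety Analysis Set". On listings it says: "All concomitant medications and therapies will be presented in patient listings".

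Protocol 7.3.2.4 provides for a by-patient listing with a wider scope: "Prior and concomitant medications will be coded to the generic term". Protocol 5.4.1 and 6.23 and SAP 3.5.3 set the recording window, from 28 days before enrollment to 30 days after the last dose. None of these sections gives a missing-date rule that would override the third bullet. SAP Section 4 declares only the efficacy analysis set as a departure from the protocol.

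**The concern.** The recording window deliberately captures medicines started before dosing. A baseline medicine that runs on past the window has no stop date within it. Both SAP definitions call that medicine concomitant, and the third bullet says it is not. A programmer cannot follow all three texts.

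What is at stake is the concomitant-medication frequency table for the Safety Analysis Set. It would under-count medicines carried into treatment, always in the same direction. The table gives context for adverse events and possible interactions, and Protocol 8.5 names concomitant medication among the factors in judging causality. SAP 2.2.1 drops the interim and primary analyses after early termination and leaves one final analysis, so no later planned analysis would correct the table.

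**Working it through.** The plan states no figure on this point. The check sets each bullet of SAP 3.1.6 against the paragraph's own definition (use on or after first dose) and against SAP 3.5.3.

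| Bullet | Start date | Stop date | Bullet's result | Against the definitions |
|---|---|---|---|---|
| 1 | on or after first dose | missing | concomitant | agrees |
| 2 | missing | on or after first dose | concomitant | agrees |
| 3 | before first dose | missing | not concomitant | conflicts for any medicine still taken at first dose |
| 4 | missing | before first dose | not concomitant | agrees |
| 5 | missing | missing | not concomitant | cannot be settled; a choice of default |

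Three bullets agree, one conflicts and one is a default.

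Records with a start before first dose divide as follows:

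- **Stop date known, on or after first dose.** Concomitant under both definitions. No conflict.
- **Ongoing, so no stop date.** Both definitions say concomitant and bullet 3 says not. This is a direct contradiction, because the lead-in covers any missing end date and makes no exception for ongoing records.
- **Stopped, date unknown.** The record alone does not show whether use reached first dose. Bullet 3 assumes that it did not. If the medicine was in fact stopped during the study, it is wrongly left out.
- **Stop date partial.** The lead-in promises rules for incomplete dates, but no bullet addresses one.

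The same section resolves unknown dates the other way for adverse events: an event with a completely missing date is counted as treatment-emergent.

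**Size.** Let m be the share of records for a continued baseline medicine that have a blank stop date. With one record per patient for the term:

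reported percentage = true percentage × (1 − m)

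The documents give neither m nor the true percentage. Taking a true percentage of 50% as an assumption:

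| m | Calculation | Reported |
|---|---|---|
| 0 | 50 × 1.00 | 50.0% |
| 0.10 | 50 × 0.90 | 45.0% |
| 0.25 | 50 × 0.75 | 37.5% |
| 0.50 | 50 × 0.50 | 25.0% |
| 1.00 | 50 × 0.00 | 0% |

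The last row is the worst case. A patient with another qualifying record under the same term is still counted, so the loss can be smaller than shown.

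**The case against.** The best defence is that the two sections can be read together. SAP 3.5.3 governs the table and expressly includes medicines continuing at first dose. SAP 3.1.6 is about missing dates, and a medicine known to be ongoing has no stop date to be missing. On that reading, bullet 3 applies only where the stop date is truly unknown. It is then a default of the same kind as bullet 5, open to debate but not contradictory.

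Part of this stands. For a stopped medicine whose date cannot be established, bullet 3 is an unsupported assumption and not a strict contradiction. If the eCRF carries an ongoing flag that takes precedence, most of the loss disappears. Protocol 9.2 leaves completion instructions to an EDC manual that is not among the documents, and it requires missing data to be accounted for. SAP 2.3.3 requires queries to be resolved, or adjudicated as unresolvable, before the final analysis. Unexplained blanks may therefore be few.

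The defence does not remove the problem. The SAP nowhere states the combined reading or mentions an ongoing flag, and the lead-in to the bullets is unqualified. Even on that reading, a baseline medicine stopped during the study with no recorded stop date is left out.

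It is also fair to say that the effect is confined to one descriptive table, and that the numerical illustration rests on assumed values.

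**Conclusion.** The rule is wrong as written. Bullet 3 contradicts both definitions for medicines ongoing at first dose with no stop date. For medicines stopped on an unknown date, it adopts a default that can only lower the counts.

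The size cannot be fixed from the documents: the loss lies between 0% and 100% of the affected records, depending on m and on whether ongoing status is handled outside the stated rule. The wording conflict is certain; the amount of under-counting in practice is not.

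The consequence is limited. ORR, DOR, PFS, OS and the adverse event counts do not use this classification. The SAP's listing sentence names only concomitant medicines, but the listing in Protocol 7.3.2.4 includes prior medicines as well, so the records stay visible there. The point should be corrected before the table is produced, but it does not threaten the trial's conclusions.

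**What to change.** Replace the third medication bullet in SAP 3.1.6 with:

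> *Where a medicine was started before first dose and is marked ongoing or has no stop date, count it as concomitant unless a partial stop date or another record shows that it ended before first dose.*

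Add a cross-reference so that 3.1.6 and 3.5.3 use one definition. It would also help to add a line for partial dates, which the lead-in promises and the bullets do not supply. Counting records with both dates missing as concomitant would be the more conservative default, but that change is optional.

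The cost is one bullet, one cross-reference and one line of derivation code, plus a short rule if partial dates are added. The drawback is that a few medicines stopped before dosing on an unknown date will be over-counted. If the SAP is not reopened, derive the table under the 3.5.3 definition and report the departure in the clinical study report, as Protocol Section 7 provides.

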### **3.1.7. Visit Windows**

#### **3.1.7.1. Definition of Study Day**

Study day is the day relative to the first dose of study drug administration. It will be calculated from the date of first dose of study drug administration and derived as follows:

- For days on or after the first dose date, assessment date – first dose date + 1

- For days prior to the first dose date, assessment date – first dose date

Therefore, study day 1 is the day of the first dose of study drug administration.

### **3.1.7.2. Analysis Visit Windows**

No analysis visit windows will be identified for the safety summaries. Visit-based data summaries will be based on the protocol scheduled visits.

If more than one assessment is available for a given post-baseline visit, the worst observation will be selected for visit-based summaries.

Any data relating to unscheduled visits will not be assigned to a particular visit or time point. However, the following exceptions will be made:

- Unscheduled visit prior to first dose of study drug may be included in the calculation of baseline value if applicable.
- Unscheduled visits after the first dose of study drug will be considered in summaries for the extreme post-baseline value.

## **3.2. Analysis Sets and Subgroups**

### **3.2.1. Efficacy Analysis Set**

All patients who receive at least one dose of tovorafenib and have measurable disease as determined by the Investigator at baseline will be considered evaluable for efficacy and included in the Efficacy Analysis Set. Efficacy-evaluable patients who don't have any post-baseline disease assessment will be considered as non-responders.

Patients in the Efficacy Analysis Set who have a best overall confirmed response of CR or PR will be evaluable for duration of response (DOR) and time to response (TTR).

### **3.2.2. Safety Analysis Set**

All patients enrolled in the study who receive at least one dose of tovorafenib will be included in the Safety Analysis Set.

### **3.2.3. Pharmacokinetic Analysis Set**

The pharmacokinetic (PK) analysis set includes all patients enrolled on this study who have at least one documented tovorafenib administration and at least one reportable PK concentration data.

### **3.2.4. Subgroup Analyses**

Due to the small sample size, subgroup analyses of key efficacy endpoints will only be performed for the following baseline variables:

- Sex (Female, Male)
- CNS tumor (Yes, No; tissue agnostic cohort)

### **3.3. Analysis Variables**

#### **3.3.1. Primary Efficacy Variable**

##### **3.3.1.1. Overall Response Rate**

The primary efficacy variable is overall response rate (ORR) defined as the proportion of patients with the best overall confirmed response of complete response (CR) or partial response (PR) according to the appropriate response assessment criteria for the disease setting as assessed by the Investigator.

Complete or partial responses will be recognized if the criteria for each are met at a subsequent scan, a minimum of 4 weeks later.

Guidance on the determination of best overall confirmed response by RECIST 1.1 and RANO response criteria are provided in Section [6.1](#) and [6.2](#) of the Appendix.

#### **3.3.2. Secondary Efficacy Variables**

##### **3.3.2.1. Duration of Response**

Duration of response (DOR) is defined as the interval from the date of the first documentation of tumor response (CR or PR) that was subsequently confirmed by investigator assessment to the date of first occurrence of radiographic disease progression based on RECIST 1.1 or RANO criteria or death due to any cause, whichever occurs earlier. If a patient does not experience progression or death by the data cutoff date, then the patient will be censored at the date of the last evaluable tumor assessment.

##### **3.3.2.2. Time to Response**

Time to Response (TTR) is defined in patients with best overall response of CR or PR as determined by Investigator. It is the interval from the date of the first dose to date of first documentation of tumor response (CR or PR) that was subsequently confirmed by investigator assessment.

##### **3.3.2.3. Progression Free Survival**

PFS is defined as the interval from the date of the first dose to the first occurrence of radiographic disease progression based on RECIST 1.1 or RANO criteria or death due to any cause, whichever occurs earlier. If a patient does not experience progression or death by the data cutoff date, then the patient will be censored at the date of the last evaluable tumor assessment. Patients who complete treatment or withdraw from treatment but do not withdraw consent from the study will continue to be followed for progression during the long-term follow-up (LTFU). Patients with no relevant tumor response assessment will be censored at the start of treatment. See Appendix 6.3 for complete censoring rules for PFS.

##### **3.3.2.4. Overall Survival**

OS is defined as the interval from the date of the first dose until the recorded date of death due to any cause. Patients who are still alive and patients lost to follow-up will be censored on the date when they were last known to be alive.

### **3.3.3. Safety Variables**

The evaluation of safety and tolerability is a secondary objective. Safety variables include clinical laboratory results, vital signs, physical examinations, visual acuity, AEs, ECOG/Lansky performance scores, 12-lead ECG, and echocardiogram/MUGA. Clinically significant abnormalities of laboratory test results or other safety assessments (eg, ECG, radiological scans, vital signs) will be reported as AEs on the CRF.

#### **3.3.3.1. Adverse Events**

All AEs will be coded using the Medical Dictionary of Regulatory Activities (MedDRA) Version 24.0 or later and will be classified by MedDRA System Organ Class (SOC) and Preferred Term (PT). Analyses of AEs will be based on the principle of treatment emergence. An AE is considered to be treatment-emergent if it has a start date/time on or after the date/time of first dose of study drug up to 30 days after the last dose of study treatment and before the start of subsequent therapy, whichever comes earlier.

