7.3.2. Safety Analyses

Safety will be assessed by clinical review of all relevant parameters, including AEs, SAEs, AESIs, laboratory values, and vital signs. Unless specified otherwise, the safety analyses will be conducted for the Safety Analysis Set defined in Section 7.1.

The reported AE term will be assigned a standardized Preferred Term using the Medical Dictionary for Regulatory Activities (MedDRA), version 24.0 or later, and adverse event severity will be graded according to National Cancer Institute (NCI) CTCAE v5.0.

Treatment-emergent adverse events will be tabulated according to MedDRA by system organ class, high level terms, and preferred terms and will be include the following categories: frequency of AEs overall, by grade, relationship to study treatment, time-of-onset, duration of the event, duration of resolution, and any concomitant medications administered. A listing of TEAEs resulting in study drug discontinuation will be provided. For reporting purpose, treatment-emergent adverse event is defined as new or worsening adverse events occurring on or after the first dose of study drug is administered until the clinical cutoff date. All safety analyses of adverse events will also include all adverse events with onset on or after the first study drug treatment until the data cutoff date.

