8. ADVERSE EVENTS

8.1. Adverse Events, Adverse Events of Special Interest, and Serious Adverse Events

Adverse events will be reported by the patient (or, when appropriate, by a caregiver, surrogate, or the patient's legally authorized representative).

The Investigator and any qualified designees are responsible for detecting, documenting, and recording events that meet the definition of an AE, AESI, or SAE and remain responsible for following up AEs that are serious, considered events of special interest, considered related to the study intervention or study procedures, or caused the patient to discontinue DAY101 or combination partner.

All AEs, whether reported by the patient or the patient's parent/legal guardian or noted by study personnel, will be recorded in the patient's medical record on the Adverse Event eCRF.

See Appendix G for instructions on collection, assessing, and reporting of AEs.

8.1.1. Time Period and Frequency for Collecting Adverse Event, Adverse Events of Special Interest, and Serious Adverse Event Information

Report all SAEs deemed related to protocol-mandated procedures from the signing of informed consent through to start of treatment with DAY101 or combination partner, whichever is administered first.

Report all AEs, AESIs, including SAEs, from the start of treatment until 30 days after the last dose of DAY101 or combination partner, whichever was administered last.

For patients who screen fail or are enrolled but do not receive study drug, the reporting period for SAEs ends 30 days after the last procedure (e.g., screening procedure).

Table 8: Summary of AE Collection Periods

Time Period	AE Collection
ICF signature to start of study drug	Protocol/procedure-related SAEs only
Start of study drug to 30 days after last study drug dose (DAY101, additional study treatment, whichever was administered last) ^a	All AEs, AESIs, and SAEs
Beyond 30 days after last study drug dose (DAY101, additional study treatment, whichever was administered last)	Any SAEs or AESIs related to study drug

Abbreviations: AE, adverse event; AESI, adverse event of special interest; ICF, informed consent form; SAE, serious adverse event.

^a See Section 8.1.3 for follow-up of AEs. If a patient begins a new anticancer therapy, the AE reporting period for non-SAEs and SAE/AESIs not related to study drug ends at the time the new treatment is started.

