## 4. DEVIATIONS FROM PROTOCOL

Definition of efficacy analysis sets, Section [3.2.1](#).

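### The SAP's 30-day/new-therapy limit on treatment emergence removes late drug-related AESIs, and probably late related SAEs, from the summary tables, and SAP Section 4 does not declare this departure from the master protocol

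*SAP*

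**What the plan says.** **Master protocol, analysis.** Section 7.3.2 defines treatment-emergent events as those "occurring on or after the first dose of study drug is administered until the clinical cutoff date". It adds that the analyses "will also include all adverse events with onset on or after the first study drug treatment until the data cutoff date". Neither sentence mentions 30 days, new therapy or causality.

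**Master protocol, collection.** Table 8 in Section 8.1.1 collects everything up to 30 days after the last dose. Beyond that point it collects "Any SAEs or AESIs related to study drug". Its footnote covers patients who move to another cancer treatment: "the AE reporting period for non-SAEs and SAE/AESIs not related to study drug ends at the time the new treatment is started".

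**SAP, definition.** Section 3.3.3.1 ends emergence "up to 30 days after the last dose of study treatment and before the start of subsequent therapy, whichever comes earlier". Section 3.1.6 gives the same limits in other words: "until 30 days after the last dose of study treatment or before the start of subsequent therapy, whichever comes first". Section 3.1.6 also requires the event to be new or worsening, which 3.3.3.1 does not. Neither section makes an exception for related events.

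**SAP, use.** Section 3.8.1 bases the adverse event analyses on treatment-emergent events. Section 3.8.3 says the same explicitly for the AESI table.

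**SAP, declared departures.** Section 4 has a single entry: "Definition of efficacy analysis sets, Section" 3.2.1. Protocol Section 7 requires the SAP to set out any departure from the protocol's planned analysis.

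**The concern.** Once the SAP window has closed, the protocol still asks for one class of event: SAEs and AESIs that the investigator attributes to study drug. The SAP's flag makes no exception for them. These events are then collected and reported to the sponsor but are absent from tables built on that flag.

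At stake are the tabulated rates of drug-related AESIs and, on the likelier reading, of related SAEs. Some AESI categories, such as secondary primary malignancies, can plausibly appear after treatment has stopped or after the patient has moved to another therapy. A listing keeps such a case visible but gives no rate. A reader of the report would also not learn from Section 4 that the analysis window differs from the master protocol's.

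**Working it through.** No design figure depends on this window, so there is nothing to reproduce. The check is to take each kind of event with onset after the SAP window and follow it from collection to output.

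| Event with onset after the window | Still collected (Protocol Table 8)? | Summary tables (SAP) | Listings (SAP 3.8.1) |
|---|---|---|---|
| AESI related to study drug | Yes | Out of the AESI table (3.8.3) | Kept |
| SAE related to study drug | Yes | Probably out of the SAE and treatment-related SAE rows (3.8.2) | Kept |
| Unrelated SAE or AESI; non-serious event that is not an AESI | No | Nothing further is due to be collected | Not applicable |
| Death | Yes, through survival follow-up (Protocol 6.21) | Kept in the all-deaths row (3.8.2) and the OS death count (3.7.3) | Kept |

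Four rows or readings need comment.

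1. **AESIs.** The loss is certain, because 3.8.3 names treatment-emergent events as its basis. The Table 8 footnote speaks of non-SAEs and could be read as also closing collection of a related but non-serious AESI at new therapy. However, Table 8's last row has no such condition, and Protocol 8.1.1 and 8.1.3 handle non-serious AESIs in the same way as SAEs. I read them as still collected.

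2. **SAEs.** Section 3.8.2 is headed as a summary of TEAEs, and 3.8.1 bases the analyses on them, which points to exclusion. But the SAE and treatment-related SAE rows lack the TEAE label that neighbouring rows carry. Exclusion is the likelier reading and is not certain.

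3. **Deaths.** The window applies to the start of the event. A fatal event that begins inside the window counts in the fatal-TEAE row even if death comes later. Only a fatal event that begins after the window leaves that row, and the death is still counted among all deaths. The OS count uses the Efficacy Analysis Set; the all-deaths row uses the Safety Analysis Set.

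4. **Direction.** Let N be the number of patients in the Safety Analysis Set. Let r be the number with at least one related event of a given type from first dose to data cutoff, and k the number of these whose only such events start after the window. For a row that uses the SAP flag, these patients contribute (r − k)/N instead of r/N. The shortfall is r/N − (r − k)/N = k/N. This is zero if k = 0 and positive otherwise, so the tabulated rate can only fall. The documents give no value for N, r or k.

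**The case against.** **The window has a rationale.** It matches the period in which the protocol collects all adverse events. Afterwards capture depends on the investigator's causality judgement and, once the patient has left the study, on the investigator happening to learn of the event (Protocol 8.1.1). Adding such events to the flag makes emergence depend on causality and mixes complete with selective ascertainment in one rate. It also does not restore Protocol 7.3.2, which has no causality condition. This stands. It is a good reason to prefer a separate post-window table, or at least a footnote. It is not a reason to leave the events untabulated.

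**The sub-protocol is not to hand.** SAP Section 1 rests on the master protocol and the DAY101-102a sub-protocol. The sub-protocol may already set the 30-day window. That would soften the charge of an undeclared change, but the conflict with master Protocol 7.3.2 would remain and Section 4 should still name it.

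**Nothing is hidden.** The listings cover all adverse events, including those that are not treatment-emergent, with day of onset. True, but the protocol places these events in the analyses.

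**Stronger readings that a reader might infer.** One is that late deaths vanish from the tables; SAP 3.8.2 and 3.7.3 both count them. Another is that late related SAEs are certainly missing from every table; the unlabelled SAE rows leave that open. A third is that the fatal-TEAE rate is broadly understated; only fatal events with post-window onset are affected. The documents support none of these.

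**Conclusion.** The point holds in a limited form. The SAP narrows the treatment-emergence window relative to master Protocol 7.3.2 without saying so in Section 4. Late drug-related AESIs drop out of the AESI table. Late related SAEs probably drop out of the SAE and treatment-related SAE summaries. Deaths are not lost.

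The size cannot be estimated, because the documents give no event counts or timings. It may be small: SAP 2.2.1 ends the study early, with patients followed for at least 6 months from first dose, which limits the time in which late events can arise. The direction is fixed, since any affected patient lowers a tabulated rate.

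The conclusion assumes that Table 8 is followed, so that late related events reach the database. For the SAE rows it also assumes that the TEAE basis in 3.8.1 governs 3.8.2. The primary endpoint is unaffected. This should be corrected because it can understate drug-related risk and is cheap to put right.

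**What to change.** 1. Keep the 30-day/new-therapy limit for unrelated events and for non-serious events that are not AESIs.
2. For SAEs and AESIs related to study drug with onset after that limit and up to data cutoff, including after new therapy, do one of two things: extend the TEAE flag to include them, or add a separate summary table of post-window related SAEs and AESIs. The separate table leaves the TEAE definition free of a causality condition.
3. State in SAP 3.8.2 and 3.8.3 which set the SAE, treatment-related SAE and AESI rows use.
4. Word the window identically in 3.1.6 and 3.3.3.1, including whether an event must be new or worsening.
5. Add the departure from master Protocol 7.3.2 to SAP Section 4.
6. Footnote that ascertainment after the window is less complete than during treatment.

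The cost is one extra condition in the flag or one extra table, plus a few lines of text. No new data are needed, since Table 8 already requires these events. Reported rates of related SAEs and AESIs may rise slightly.
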